FLT3-Mutation Negative (MN)	For the purpose of this study FLT3-MN is defined as the absence of ITD mutation and absence of TKD activating mutation at codons D835 and I836 in the FLT3 gene (FMS-like tyrosine kinase 3 gene), based on mutant to wild type signal ratio below the 0.05 clinical cutoff.
Investigational drug	The study treatment whose properties are being tested in the study; this definition is consistent with US CFR 21 Section 312.3 and is synonymous with "investigational new drug."
Investigational treatment	Drug whose properties are being tested in the study as well as their associated placebo and active treatment controls (when applicable). This also includes approved drugs used outside of their indication/approved dosage, or that are tested in a fixed combination. Investigational treatment generally does not include other study treatments administered as concomitant background therapy required or allowed by the protocol when used in within approved indication/dosage
Medication number	A unique identifier on the label of each study treatment package which is linked to one of the treatment groups of a study
Other study treatment	Any drug administered to the patient as part of the required study procedures that is not included in the investigational treatment
Subject number (Subject No.)	A unique identifying number assigned to each patient/subject/healthy volunteer who enrolls in the study
Period	A subdivision of the study timeline; divides stages into smaller functional segments such as screening, induction, consolidation, post-consolidation, follow-up for efficacy or survival.
Personal Data	Subject information collected by the Investigator that is transferred to Novartis for the purpose of the clinical trial. This data includes subject identifier information, study information and biological samples.
Randomization number	A unique treatment identification code assigned to each randomized patient, corresponding to a specific treatment arm assignment
Stop study participation	Point/time at which the patient came in for a final evaluation visit or when study treatment was discontinued whichever is later
Study treatment	Midostaurin or placebo in sequential combination with daunorubicin/idarubicin and cytarabine induction, in sequential combination with intermediate dose cytarabine consolidation, and as single agent post-consolidation therapy.

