6.1 Study treatment

In this study, the term “Study drug” refers to midostaurin/placebo labeled as PKC412/placebo provided as 25 mg capsules which are packaged in blister packs and supplied by Novartis as double-blind supplies.

The term “Study treatment” will indicate treatment with daunorubicin/idarubicin, cytarabine, or midostaurin/placebo.

Induction chemotherapy will start on Day 1 and the randomization and treatment start with midostaurin/placebo will be done on Day 8 when (molecular) eligibility has been confirmed based on the absence of a FLT3 mutation as determined by a Novartis designated laboratory. If the patient does not have FLT3 test results qualifying for eligibility by Day 8 then the patient will be considered as a molecular screening failure and cannot be randomized.

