6.3 Dose modifications

6.3.1 Dose modification and dose delay

For patients who do not tolerate the protocol-specified dosing schedule, dose interruptions and/or reductions are either recommended or mandated in order to allow patients to continue the study treatment.

These dose modifications are summarized in [Table 6-2](#). Deviations to mandatory dose interruptions and/or reductions are not allowed. Permanent treatment discontinuation is mandatory for specific events indicated as such in [Table 6-2](#).

These dose changes must be recorded on the appropriate CRF.

Study drug (midostaurin/placebo)

[Table 6-2](#) describes toxicities (i.e., adverse drug reactions), laboratory values, or other assessments that require interruption or dose modification of study drug. Whether an AE that is not considered to be caused by the study treatment requires modifications needs to be assessed by the investigator. The need for modification in case of non-drug related AEs depends on the type of these AEs.

During induction and consolidation therapies, modifications must be done in case of non-hematologic toxicities, i.e., ADRs (pulmonary, cardiac or other non-hematologic toxicities).

During post-consolidation therapy, modifications must be done in case of hematologic and non-hematologic toxicities (pulmonary, cardiac or other non-hematologic toxicities).

If interruptions occur, missed doses of study drug will not be made up.

Study drug interruptions of greater than 28 consecutive days will require discontinuation from study treatment, unless the patient undergoes HSCT as in that case the drug interruption can be longer than 28 consecutive days (please refer to section 6.1.1 for more detailed information).

Cytarabine

Doses will be modified only during the consolidation phase with intermediate-dose cytarabine and in case of neurotoxicity, hematology and non-hematology toxicity. Please refer to [Table 6-2](#).

Idarubicin/ Daunorubicin

Doses will be modified during induction phase in case of hepatotoxicity, hematology and non-hematology toxicity. Please refer to [Table 6-2](#).

[figure not shown]
[figure not shown]
[figure not shown]

Table 6-2 Criteria for dose reduction/interruption and re-initiation of midostaurin/placebo, daunorubicin/idarubicin and cytarabine treatment for adverse drug reactions

[figure not shown]
Dose modifications for midostaurin/placebo	
Hematologic toxicities	

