During induction and consolidation cycles	No dose modifications are required for hematologic toxicity due to midostaurin/placebo during induction and consolidation therapy.
During post-consolidation cycles	In the presence of grade 4 neutropenia during post-consolidation therapy, midostaurin/placebo must be held until Absolute Neutrophil Count (ANC) $\geq 1.0 \times 10^9/L$. Once ANC $\geq 1.0 \times 10^9/L$, then resume midostaurin/placebo at the previous dose. If neutropenia persists for more than two weeks, then discontinue midostaurin/placebo protocol therapy.
Non-Hematologic toxicities:	

 Pulmonary toxicities 	
During induction, consolidation and post-consolidation cycles	For \geq grade 3 pulmonary infiltrate , midostaurin/placebo must be interrupted for the remainder of the cycle. Resume midostaurin/placebo at the same dose when infiltrate resolves to \leq grade 1. Missed doses of midostaurin/placebo will not be made up. If there is no improvement after 28 days, the patient must be discontinued from study drug.

 Cardiac Toxicity 	
During induction, consolidation and post-consolidation cycles	
 For QTcF interval > 470 ms and ≤ 500 ms, check magnesium and potassium levels and correct any abnormalities. If possible, stop any medications that may prolong the QTcF interval. Decrease midostaurin/placebo to 50 mg once daily for the remainder of the cycle. Resume midostaurin/placebo at the initial dose in the next cycle provided that QTcF interval improves to ≤ 470 ms at the start of that cycle. Otherwise continue midostaurin/placebo 50 mg once daily. For QTcF interval > 500 ms and/or QTcF prolongation >60 ms from baseline, check magnesium and potassium levels and correct any abnormalities. Hold or interrupt midostaurin/placebo for the remainder of the cycle, and, if possible, stop any medications that may prolong the QTcF interval. If QTcF improves to ≤ 470 ms just prior to the next cycle, resume midostaurin/placebo at the initial dose. If QTcF interval is not improved to ≤ 470 ms in time to start the next cycle, midostaurin/placebo may be held up to 28 days. If there is no improvement after 28 days, the patient must be discontinued from study drug.

 Other Non-Hematologic toxicity 	

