
During induction and consolidation cycles
 
During post-consolidation cycles
	
 • Grade 1/2: No dose modifications for any grade 1 or 2 non-hematologic toxicity. • Grade 3/4: If a patient experiences other grade 3/4 non-hematologic toxicity considered related to midostaurin/placebo, midostaurin/placebo will be interrupted until toxicity resolves to \leq grade 1. If the toxicity resolves prior to day 21, then restart at same dose to complete current cycle. Missed doses of midostaurin/placebo will not be made up. A study drug interruption in excess of 28 days will require discontinuation of study treatment. • Grade 1/2: Persistent grade 1 or 2 toxicity during post-consolidation therapy that patients deem to be unacceptable may prompt a study drug interruption for as long as 28 days. A study drug interruption in excess of 28 days will require discontinuation of study treatment. • Grade 3/4: For other grade 3/4 non-hematologic toxicities that are considered to be related to midostaurin/placebo, interrupt midostaurin/placebo. Resume midostaurin/placebo at the same dose when toxicity resolves to \leq grade 2. If midostaurin/placebo is held for more than 28 days, then discontinue midostaurin/placebo post-consolidation therapy.

Dose modifications for intermediate-dose cytarabine (IDAC) induction 2 if applicable and consolidation therapy
	

During Induction 2 if applicable and consolidation cycles
	
Dose reduction according to institutional guidelines except in case of neurotoxicity dose modifications as below: Contributions of concomitant medications to neurotoxicity should be assessed and other medications discontinued if possible.
 
For neurotoxicity \geq grade 2 due to intermediate-dose cytarabine, discontinue cytarabine for the remainder of the cycle. Intermediate-dose cytarabine may be considered at the next consolidation therapy cycle with a dose modification from 1500mg/m² to 1000mg in patients <60 years of age and from 1000mg/m² to 600mg/m² in patients \geq60 of age if the toxicity has resolved to \leq grade 1.
 
For a second occurrence of neurotoxicity \geq grade 2, intermediate-dose cytarabine should be permanently discontinued.

Dose modifications for daunorubicin		
	Dose reduction according to institutional guidelines except in case of hepatotoxicity dose modifications as below:	
During induction cycles	Total Bilirubin (mg/dL)	% daunorubicin dose to administer
	≤ 1.2	100%

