6.3.2 Dose adjustments for QTcF prolongation

In case of QTcF >500 ms, (or QTcF prolongation >60 ms from baseline)

1. Assess the quality of the ECG recording and the QT value and repeat if needed
2. Interrupt study treatment
3. Determine the serum electrolyte levels (in particular hypokalemia, hypomagnesemia). If abnormal, correct abnormalities before resuming study drug treatment.
4. Review concomitant medication associated with QT prolongation, including drugs with a “Known”, “Possible”, or “Conditional risk of Torsades de Pointes”, and drugs with the potential to increase the risk of study drug exposure related QT prolongation
5. Check study drug dosing schedule and treatment compliance
6. Consider collecting a time-matched PK sample, and record time and date of last study drug intake.
7. Note that measurements of QTcF ≥ 480 ms shall be centrally verified on a copy of the original high quality recording that includes time and voltage scales

After confirming ECG reading at site, if QTcF > 500 ms

- Interrupt study treatment
- Repeat ECG and confirm ECG diagnosis by a cardiologist
- If QTcF confirmed > 500 ms:
 - Correct electrolytes, eliminate culprit concomitant treatments, and identify and address clinical conditions that could potentially prolong the QT
 - Consult with a cardiologist (or qualified specialist)
 - Increase cardiac monitoring as indicated, until the QTcF returns to ≤ 470 ms.
- After resolution to ≤ 470 ms, consider re-introducing treatment at reduced dose, and increase ECG monitoring for the next treatment(s):
 - If QTcF remains ≤ 500 ms after dose reduction, continue planned ECG monitoring during subsequent treatment
 - If QTcF recurs > 500 ms after dose reduction, discontinue patient from study drug.

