6.4.3 Prohibited concomitant therapy

Strong CYP3A4 inducers: Concomitant use of midostaurin/placebo with strong inducers of CYP3A4 should be avoided. Strong CYP3A4 inducers decrease exposure of midostaurin and its active metabolites (CGP52421 and CGP62221). In a study in healthy subjects, coadministration of the strong CYP3A4 inducer rifampicin (rifampin, 600 mg daily) to steady state with a single dose of midostaurin decreased midostaurin C_{max} by 73% and -AUC_{inf} by 96% in average, respectively. CGP62221 exhibited a similar pattern. The mean AUC_{last} of CGP52421 decreased by 60%. In absence of clinical data, the impact of strong CYP3A4 inducers on midostaurin exposure at steady-state was investigated based on physiologically-based PK models. Exposure was predicted to be decreased by 60%.

A list of strong inducers of CYP3A4 is available in [Appendix 1](#).

Other prohibited concomitant medications: If concomitant administration of drugs with a “known risk of torsades de pointes (TdP)” is required and cannot be avoided, then the study drug must be interrupted. If, based on the investigator assessment and clinical need, study treatment is resumed, close ECG monitoring is advised. Note that measurements of QTc_≥480ms shall be centrally verified on a copy of a high quality recording that includes time and voltage scales.

If during the course of the study, concomitant administration of a drug with “Possible risk of TdP” or “Conditional risk of TdP” is required, based on the investigator assessment and clinical need, study treatment may be continued with close ECG monitoring to ensure patient safety. A list of drugs associated with QT prolongation and/or TdP is available online at [www.qtdrugs.org].

As far as possible avoid co-administering drugs with a “Known”, “Possible”, or “Conditional” risk of TdP during the course of the study:

- If concomitant administration of drugs with a “Known risk of TdP” is required and cannot be avoided, study drug must be interrupted. If, based on the investigator assessment and clinical need, study treatment is resumed, close ECG monitoring is advised.
- If during the course of the study, concomitant administration of a drug with “Possible risk” or “Conditional risk of TdP” is required, based on the investigator assessment and clinical need, study treatment may be continued under close ECG monitoring to ensure patient safety.

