7.1.6 Follow up for safety evaluations

[figure not shown]
All patients must have safety evaluations for 30 days, after the last dose of study treatment (including cytarabine, daunorubicin/idarubicin or midostaurin/placebo).

Data collected should be added to the Adverse Events CRF and the Concomitant Medications CRF.

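### After more than 28 days off study drug in induction or consolidation, 6.3.1 and one row of Table 6-2 end study treatment (which includes chemotherapy), while the pulmonary and QTcF >500 ms rows end study drug

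*Protocol*

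**What the plan says.** Section 6.3.1 sets a general limit on holds of midostaurin/placebo: "Study drug interruptions of greater than 28 consecutive days will require discontinuation from study treatment, unless the patient undergoes HSCT". In Table 6-2, the induction and consolidation entry for other grade 3/4 non-hematologic toxicity related to midostaurin/placebo repeats it: "A study drug interruption in excess of 28 days will require discontinuation of study treatment".

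Two other rows of Table 6-2 cover induction, consolidation and post-consolidation: pulmonary infiltrate of grade 3 or higher, and QTcF above 500 ms and/or prolonged by more than 60 ms from baseline. Both end differently: "If there is no improvement after 28 days, the patient must be discontinued from study drug".

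The two terms are defined. Section 6.1 limits *study drug* to midostaurin/placebo and says that *study treatment* "will indicate treatment with daunorubicin/idarubicin, cytarabine, or midostaurin/placebo". The glossary entry for study treatment begins "Midostaurin or placebo in sequential combination with daunorubicin/idarubicin and cytarabine induction, in sequential combination with intermediate dose cytarabine consolidation". Section 7.1.6 counts the chemotherapy drugs as study treatment when it dates safety follow-up, and SAP 3.2 draws the same line between the two terms.

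**The concern.** Each passage tells the site what to stop once midostaurin/placebo has been off for about four weeks, but they name different things. In induction and consolidation the difference is whether the protocol's cytarabine (and, in induction, the anthracycline) goes on. A site that applies 6.3.1 by its defined terms ends all protocol therapy because of toxicity attributed to the add-on drug. A site that follows the pulmonary or QTcF row ends midostaurin/placebo.

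Sites have little room to settle this by judgement. Section 6.3.1 makes permanent discontinuation mandatory for the events marked that way in Table 6-2, 7.1.4 requires study treatment to stop for adverse events under circumstances set out in 6.3, and Section 12 allows no authorized deviations. What is at stake is uniform patient management between sites.

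**Working it through.** No formula applies. The check sets the passages side by side, applies the definitions, and then weighs what was probably meant.

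**1. The rules**

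| Place | Phases | Trigger | What is discontinued |
|---|---|---|---|
| 6.3.1 | not limited by phase; HSCT excepted | study drug off for more than 28 consecutive days | study treatment |
| Table 6-2, other non-hematologic, grade 3/4 | induction, consolidation | study drug off for more than 28 days | study treatment |
| Table 6-2, pulmonary infiltrate, grade 3 or higher | all three | no improvement after 28 days | study drug |
| Table 6-2, QTcF >500 ms and/or >60 ms from baseline | all three | no improvement after 28 days | study drug |

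**2. Applying the definitions**

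- Patient A is in consolidation with a grade 3 infiltrate, no improvement, and midostaurin/placebo off for more than 28 days. The pulmonary row stops midostaurin/placebo. Section 6.3.1 stops study treatment, and so cytarabine as well.
- Patient B is the same, but held for QTcF above 500 ms. The result is the same.
- Patient C is held for another related grade 3/4 toxicity. Both 6.3.1 and the row say study treatment, so by definition the chemotherapy stops too.
- In post-consolidation, midostaurin/placebo is the only treatment given, so the two terms lead to the same action.

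**3. What follows on each reading**

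If study treatment is discontinued, an end-of-treatment visit is due within 7 days (7.1.3) and response is then assessed every 12 weeks (4.2.4). If only midostaurin/placebo is discontinued, the natural inference is that chemotherapy cycles continue with a response assessment between Day 21 and Day 28 of each (7.2.1). That is an inference, because no passage states it.

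**4. Evidence on intent**

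For study drug:
- The 6.3.1 sentence stands under a subheading for midostaurin/placebo, and cytarabine and idarubicin/daunorubicin have their own paragraphs after it.
- The other non-hematologic row stands in the block of Table 6-2 for midostaurin/placebo modifications. The separate chemotherapy blocks mention no 28-day stop tied to study drug.
- The definition in 6.1 joins the components with *or*.
- The terms are used loosely elsewhere. For a QTcF event, 6.3.2 says "Interrupt study treatment" where Table 6-2 holds midostaurin/placebo. Section 6.4.3 uses both terms for one hold and restart: "study drug must be interrupted. If, based on the investigator assessment and clinical need, study treatment is resumed".
- The example in SAP 3.6 has midostaurin ending on 15 April 2019 and cytarabine on 17 May 2019, which is 15 + 17 = 32 days later. It only illustrates a date rule, but it fits poorly with a literal 6.3.1.

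For the literal reading:
- The glossary and SAP 3.2 include the chemotherapy without ambiguity.
- Section 7.1.4 describes the stops under 6.3 collectively as stops of study treatment.
- The wording appears in two separate places.

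None of these passages says which wording prevails.

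**The case against.** The strongest reply is that this is loose wording rather than an instruction to stop chemotherapy. The headings place both sentences under midostaurin/placebo, chemotherapy has its own rules, and a sensible investigator would read study drug. In addition, the pulmonary and QTcF rows never say that only study drug stops or that chemotherapy continues. They set a minimum action, so a site could obey every passage by stopping everything. Finally, ending study treatment does not end care: the chemotherapy drugs are approved and may be sourced locally (6.1.1), and antineoplastic therapy after discontinuation is expected and recorded (4.2.4, 7.1.7).

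Much of this stands. Study drug is the likelier intent, the passages are not in strict logical contradiction, and nothing bars chemotherapy outside the protocol. It does not remove the point. The only course that satisfies every passage literally is to end protocol chemotherapy, which is probably the course that was not intended. Recovering the intent requires setting a defined term aside in a mandatory rule.

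A reader might also infer that the passages conflict on timing, because 6.3.1 counts elapsed days while two rows wait for lack of improvement. The documents do not require that reading. If 6.3.1 is taken as an outer limit and the 28 days run from the start of the hold, the site stops at whichever limit comes first and the timing difference largely disappears.

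**Conclusion.** The point holds as a difference in scope between mandatory stopping rules, limited to induction and consolidation. Read by its defined terms, 6.3.1 ends protocol chemotherapy after more than 28 days off midostaurin/placebo, while two rows of Table 6-2 for the same phases end midostaurin/placebo. It should be fixed, because it decides whether protocol chemotherapy continues and costs almost nothing to correct. The conclusion rests on sites applying the defined terms as written and on no other text setting precedence.

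Two stronger readings are not supported. One is that the protocol means to withdraw chemotherapy from these patients, or leaves them without it; the context points the other way, and treatment outside the protocol remains open. The other is that the trial's results are affected. The documents give no frequency for holds this long and no basis for a difference between arms, so no effect on EFS, arm balance, power or alpha can be derived, and none is claimed.

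**What to change.** In 6.3.1 and in the induction/consolidation row for other non-hematologic grade 3/4 toxicity, replace *study treatment* with *study drug (midostaurin/placebo)*. If the sponsor does intend protocol chemotherapy to stop, keep the term and say so identically in the pulmonary and QTcF rows. Optionally, add one sentence stating that the 28 days run from the start of the hold.

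The cost is one term in two places. No procedures, patients or analyses are added, and post-consolidation management does not change. SAP Section 1 records that the study stopped for futility on 23-Sep-2019 and that most patients then discontinued, while some continued planned treatment. At that stage the practical gain is limited to those still in induction or consolidation and to any later protocol that reuses this text.

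### The QTcF restart rule ignores the rise from baseline that triggered the hold, and Table 6-2 and Section 6.3.2 disagree on the dose after a reading above 500 ms

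*Protocol*

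**What the plan says.** Two places in the protocol govern QTcF prolongation.

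**Table 6-2 (Section 6.3.1), Cardiac Toxicity.** The first bullet covers QTcF above 470 and up to 500 ms: "Decrease midostaurin/placebo to 50 mg once daily for the remainder of the cycle". The second bullet sets the hold: "For QTcF interval > 500 ms and/or QTcF prolongation >60 ms from baseline". Under it, study drug stops for the rest of that cycle and electrolytes and co-medication are addressed. Restart follows one test: "If QTcF improves to ≤ 470 ms just prior to the next cycle, resume midostaurin/placebo at the initial dose". The extended hold uses the same value: "If QTcF interval is not improved to ≤ 470 ms in time to start the next cycle, midostaurin/placebo may be held up to 28 days". Without improvement after 28 days the patient comes off study drug.

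**Section 6.3.2.** It repeats the two-part trigger (>500 ms, or a rise >60 ms) and tells the site to interrupt treatment. For a confirmed reading above 500 ms it then says: "After resolution to ≤ 470 ms, consider re-introducing treatment at reduced dose", with closer ECG monitoring on re-treatment. It names no dose level. It ends: "If QTcF recurs > 500 ms after dose reduction, discontinue patient from study drug". It gives no restart test for a rise above 60 ms that never passed 500 ms.

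Section 7.2.2.7.1 sends the reader to Section 6.3 as a whole for QT-related dose adjustment, and no text ranks Table 6-2 against Section 6.3.2.

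**The concern.** A hold rule and its release rule should be tested on the same quantities. Here the hold has an absolute limb and a change limb, each sufficient on its own, but the release has only the absolute limb. A patient held because of the change can be released while that change persists. The table then instructs the site to restart the full dose at a value for which it also instructs a hold.

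The second problem is the dose after a confirmed reading above 500 ms. One section gives a direct instruction for the initial dose. The other contemplates only a reduced one and attaches its discontinuation rule to that reduction.

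At stake is consistent handling of a cardiac safety signal. Two sites with the same ECG can act differently: one restarts at full dose, the other keeps holding and may reach the 28-day discontinuation. After a second reading above 500 ms, whether the patient must stop depends on which section the site followed. Section 6.3.1 forbids deviation from mandatory interruptions, so a site facing the conflict cannot simply choose.

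**Working it through.** The plan states no figure to reproduce here. The check compares the rules directly.

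**Inputs.** Hold trigger, restart value and 28-day limit: Table 6-2. Reduced-dose restart and recurrence rule: Section 6.3.2. Initial dose, 50 mg twice daily: Section 6.1.1.1. Baselines below are illustrative, because the documents give no distribution of baseline QTcF.

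**Part 1: hold against release.** Let b be baseline QTcF and Q the reading just before the next cycle.

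- Hold: Q > 500, or Q − b > 60.
- Release: Q ≤ 470.
- Both true: b + 60 < Q ≤ 470. This range is non-empty only if b < 470 − 60 = 410.
- In whole ms, the number of such readings is 410 − b, and the largest residual rise is 470 − b.
- A two-part release test would have the ceiling min(470, b + 60).

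| Baseline (ms) | Readings meeting both rules | Count | Largest residual rise (ms) | Ceiling under a two-part test |
|---|---|---|---|---|
| 380 | 441–470 | 30 | 90 | 440 |
| 390 | 451–470 | 20 | 80 | 450 |
| 400 | 461–470 | 10 | 70 | 460 |
| 409 | 470 | 1 | 61 | 469 |
| 410 or above | none | 0 | – | 470 |

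The counts show where the conflict can occur. They are not frequencies.

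Two cases at baseline 390 ms, both genuine improvements to 470 ms or less:

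- Held at 458 ms (458 − 390 = 68). Pre-cycle 452 ms (452 − 390 = 62). Restart permitted; hold trigger still met.
- Held at 505 ms (505 − 390 = 115). Pre-cycle 465 ms (465 − 390 = 75). Same result.

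With release requiring both Q ≤ 470 and Q − b ≤ 60, no reading satisfies hold and release together at any baseline.

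**Part 2: after a confirmed reading above 500 ms.**

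| Question | Table 6-2 | Section 6.3.2 |
|---|---|---|
| Value needed to restart | ≤470 ms | ≤470 ms |
| Restart dose | Initial: 50 mg × 2 = 100 mg/day | Reduced, level not named |
| Second episode >500 ms | Hold again; each hold limited to 28 days, no rule on repeats | Discontinue, if the dose had been reduced |

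If the reduced dose means the only reduced level in Table 6-2 (an assumption), it is 50 mg × 1 = 50 mg/day, half the initial dose. A patient restarted at 100 mg/day is not covered by the recurrence rule in Section 6.3.2, and Table 6-2 supplies none.

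**The case against.** The best defence is that Table 6-2 is sequential: trigger, hold, then a specific test before the next cycle. On that reading the restart sentence governs a patient already held, 470 ms is the sponsor's chosen return value throughout, and a baseline-relative release is only a reviewer's preference. The sequence is there, but this reading does not remove the problem. It means that full dose resumes at a value that requires a hold as soon as the standing trigger is applied to it. The table's closing note, which bases modifications on the worst preceding toxicity, supports holding rather than merely reducing when the two bullets overlap, but it sets no release value.

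For the restart dose, Section 6.3.2 can be read as the specific rule for the confirmed >500 ms subset, and its wording is permissive. That softens the conflict, but precedence is not stated, and Section 6.3.2 describes no full-dose path.

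The safeguards are real. Section 6.3.2 calls for electrolyte correction and co-medication review; above 500 ms it adds cardiologist confirmation and consultation. Table 7-7 schedules pre-dose ECGs on Day 4 of each consolidation cycle, before the first post-consolidation cycle and on Day 1 of post-consolidation cycles 2 to 12. Section 6.3.1 requires discontinuation after more than 28 consecutive days off drug, HSCT excepted.

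Three stronger readings are therefore not supported:

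- **That patients are re-exposed without monitoring.** A reader might infer this from "Increase cardiac monitoring as indicated, until the QTcF returns to ≤ 470 ms". But the same section also increases ECG monitoring once treatment is re-introduced.
- **That an unchanged reading releases the hold.** Where the hold began at 470 ms or less, a reader might infer this. The restart sentence asks for improvement, and the point does not depend on that case.
- **That holds may run indefinitely.** Each hold is capped at 28 days; only the handling of repeat episodes is left open.

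**Conclusion.** Both parts hold, as defects in the wording of a dosing safety rule, and both should be corrected.

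Part 1 is exact: the overlap exists for every baseline below 410 ms and for none at or above it. Part 2 is a plain mismatch between the two sections, with the consequence that the recurrence rule misses patients restarted at the initial dose.

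The practical size is unknown. The number of patients affected cannot be derived from the documents, and the twofold dose difference rests on the assumption that the unnamed reduced dose is 50 mg once daily. Sample size, type I error and power are unaffected. The SAP Introduction records that the study stopped for futility while some patients continued protocol treatment. That limits the remaining reach but does not correct the rule.

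**What to change.** **Release test.** After any hold in which the rise exceeded 60 ms, require both QTcF ≤470 ms and a rise of no more than 60 ms from baseline before restart. Use the same test for the extended hold and the 28-day discontinuation. State which ECG is the baseline for dosing decisions. SAP Section 9.4 offers a definition: pre-dose Cycle 1 Day 1, otherwise the most recent pre-treatment day within 14 days.

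**Restart after a confirmed reading above 500 ms.** Name one dose in both Table 6-2 and Section 6.3.2, for example 50 mg once daily, the only reduced level in the table. Require discontinuation on any recurrence above 500 ms after restart, whatever the dose.

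**Cost.** Protocol wording, or an investigator letter. Table 7-7 has no row for Induction 2, but the existing restart test already needs a reading before each next cycle, so the two-part test adds no ECG to that requirement. The clinical price is longer holds, and some discontinuations at absolute values of 470 ms or less in patients with low baselines. For example, a patient with baseline 380 ms who stays at 442 ms (+62) would stop after 28 days, although 442 ms lies below the lowest absolute QTc band summarised in the SAP (>450 ms). The sponsor should accept that consequence explicitly when adopting the rule.
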